3.1 Determination of Sample Size

We will recruit up to 28 participants, including up to 6 pilot participants. Previous research with subjective ratings has repeatedly shown that data collected with 15-25 participants can yield significant results. Since participants do not need to visit the research site, participants will be recruited from both locations as available.

Statistical criteria of termination of trial

If results for sound quality ratings are significant after 15 participants completed the rating, we will consider terminating the data collection.

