3.2 Planned Analyses

3.2.1 Datasets to be analyzed, analysis population

- Analysis population: 15-25 participants
- Evaluation group: rating per setting
- Data sets: subjective ratings
- Additional analyses:
 - individual preferences and their potential dependencies, such as hearing loss, acoustic scenes and previous amplification strategies
 - correction for repeated measures.

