3.2.2 Primary Endpoint Analysis

Automatic data analysis is available in the survey tool and will be used throughout the data collection for interim analysis. The study manager will analyze the collected data set in R Statistics after the data collection completed. Microsoft Excel may be used for arranging data and plotting data sets.

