3.2.4 Interim Analysis

Automatic data analysis is available in the survey tool and will be used throughout the data collection for interim analysis. Data will be adjusted for repeated measures.

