3.3 Handling of missing data and drop-outs

Drop-outs will be replaced if possible (depending on participant availability and schedule). Smaller data sets will be analyzed if the data is complete for sub-sets of the investigation.

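### Does it matter that the plan never says whether the pilot participants count toward the 15 completers or the 15-25 analysed?

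*Combined protocol and SAP*

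**What the plan says.** Section 3.1 sets recruitment: "We will recruit up to 28 participants, including up to 6 pilot participants". It justifies the size by precedent: "Previous research with subjective ratings has repeatedly shown that data collected with 15-25 participants can yield significant results". The stopping criterion in the same section reads "If results for sound quality ratings are significant after 15 participants completed the rating, we will consider terminating the data collection". Section 3.2.1 gives the population only as a range, "Analysis population: 15-25 participants", with no inclusion rule.

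On access to results, 3.2.2 states "Automatic data analysis is available in the survey tool and will be used throughout the data collection for interim analysis", and 3.2.4 repeats this. The only adjustment named in 3.2.4 is "Data will be adjusted for repeated measures". Section 3.3 covers drop-outs, which are replaced where availability allows, and incomplete data. It does not mention pilots.

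Pilots therefore appear once, as part of the recruitment total. The document does not say whether their ratings are pooled, whether they use the final survey and stimuli, or whether they count toward the 15.

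**The concern.** Two things make this look like a fault.

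- **The counts seem to disagree.** Section 3.1 includes pilots in the recruitment total and then sets the look at 15 participants, so a literal reader may count pilots there. The ceiling of 25 in 3.2.1 cannot hold all 28 recruits. If pilots counted at the look and were then dropped from the analysis, a stop at 15 with 6 pilots would leave 15 − 6 = 9 analysed, below the stated minimum.
- **The definition is open while results can be seen.** Stopping depends on significance, and interim analysis runs throughout collection. Up to 6 of the 15 people at the look (40%) could be counted in or out once the effect of doing so is known. That would give a second chance of a false positive in a study whose results will be used to propose compression settings.

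**Working it through.** **Inputs from the plan.** Maximum recruited 28; pilots 0 to 6; look at 15 completers (all 3.1); analysed 15-25 (3.2.1). The plan gives no alpha, effect size, standard deviation, power or drop-out rate, so there is no sample-size calculation to reproduce.

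**Step 1: the counts.** Non-pilot maximum = 28 − number of pilots.

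| Pilots | Non-pilots at full recruitment | Within 15-25? |
|---|---|---|
| 0 | 28 | no |
| 3 | 25 | yes |
| 4 | 24 | yes |
| 5 | 23 | yes |
| 6 | 22 | yes |

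With 3 to 6 pilots, excluding them fits 3.2.1. Including them exceeds 25 only if all 28 are recruited and more than 25 complete. The figures do not settle the rule, but they do not conflict: one number caps recruitment and the other describes who is analysed. The 15 in the stopping criterion is also the lower end of the analysis range, so the natural reading is one population for both. The case of 9 analysed needs all 6 pilots among the first 15 and a different rule at each stage, which no section states.

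**Step 2: the error from an open rule.** Assumptions: no true difference, one paired contrast with normal differences, one-sample t-tests at two-sided 5%, 28 recruited, 6 pilots enrolled first, and the favourable set always taken. Each figure comes from 400,000 simulated data sets; repeat runs agree within about 0.1 percentage point.

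| Tests, any one significant | False-positive rate |
|---|---|
| Look at 15, rule fixed (in or out) | 5.0% |
| 15 rated: pilots in (n = 15) or out (n = 9) | 8.2% |
| Final only: pilots in (n = 28) or out (n = 22) | 7.2% |
| Pilots in at 15 rated, or out at 21 rated (n = 15 each) | 8.9% |
| Pilots fixed in, looks at 15 and 21 | 7.6% |
| Pilots fixed in, look at 15, final at 28 | 8.3% |
| Pilots fixed out, look at 15, final at 22 | 7.8% |
| Either rule at look and final (four tests) | 12.7% |
| Pilots fixed in, looks at 15, 21 and 28 | 9.8% |
| Pilots fixed in, test after every completer from 15 to 28 | 13.1% |

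**Step 3: what belongs to pilot status.** The 8.9% compares a test after 15 people have been rated with one after 21, since 15 non-pilots plus 6 pilots is 21. It therefore contains a second look. Compared at the same times:

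- looks at 15 and 21: 8.9 − 7.6 = 1.3 points;
- looks plus final: 12.7 − 9.8 = 2.9 points;
- choice at 15 rated, no extra look: 8.2 − 5.0 = 3.2 points;
- choice at the final only: 7.2 − 5.0 = 2.2 points.

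The open rule is worth about 1 to 3 points at most. Testing after every completer with the pilot rule fixed (13.1%) costs more than leaving the rule open with one look and a final test (12.7%). The main source of error is repeated unadjusted looking, which is a separate matter.

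**The case for a change.** The best case for a change is that it is nearly free: one sentence in 3.1 and a matching figure in 3.2.1 would close the question before any result exists. Blinding does not close it, because a p-value shows which choice is favourable without revealing any setting. Adjusting for repeated measures is not described as covering the choice of population. Exclusion of pilots by convention is not written down, and 3.1 does include them in its total. Reading 25 as 28 less about 3 drop-outs is a guess.

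All of this stands as description: the definition is missing, and a selective analyst could gain from that. It does not show that the plan as written leads to a wrong analysis. The inflation needs an analyst who computes both versions and reports the better one, and no section provides for that. The documents do not say who sees the interim output, and 3.1 commits only to considering a stop. Nor does the case identify which rule is correct, since inclusion and exclusion are both defensible. A rule that depends on whether the survey changed after piloting would still leave pilot status to a decision taken once pilot ratings exist. Finally, 1.1 sends the resulting settings to an in-person follow-up study, so a chance finding would meet a further test.

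**Conclusion.** No change follows. The plan leaves the status of up to 6 pilots unstated, but its figures are compatible, and excluding 6 pilots gives at most 22, inside 15-25. An analyst who applies either usual rule to the look and to the final analysis alike has a coherent population, and a single test stays at 5.0% either way. No rule that the plan does state gives a wrong result because of this gap.

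The worst case attributable to pilot status is about 1 to 3 percentage points of false-positive rate. That rests on an assumed two-sided 5% level, a single paired contrast, 6 pilots enrolled first and consistent selection of the favourable set; the plan supplies none of these except the maximum of 6. The figures of 8.9% and 12.7% should not be charged to pilots alone, because they include an additional look. That the gap exists is certain from the text; its size is illustrative only.

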2.2 Procedures

2.2.1 Investigation-related Procedure

The study is conducted remotely, so a potential participant's eligibility will be determined based on audiograms on file. If the study site doesn't have a participant's audiogram on file, the potential participant can request their HCP to release an audiogram to a study site.

After successful completion of the screening call, participants will sign the consent form and complete the demographic questionnaire over the phone. Afterwards, they will receive a package with a tablet and headphones and will get on another call with the researcher to conduct the subjective rating via an online sound survey tool.

The subjective rating will include rating of reverberation, sound source separation, sound source localization, overall preference ranking and an A/B test for preference. The stimuli consist of speech in quiet, speech in noise, reverberant speech, and music recorded with different hearing aids and hearing aid settings (hearing aids set to fast and slow compression settings, default

compression setting, a competitor's hearing aid and unaided), post-processed for headphone presentation and incorporated in an online sound survey.

3 Statistical design and analysis

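### The plan allows a stop when ratings are significant at 15 participants, with no alpha, boundary or limit on looks; followed with unadjusted 5% tests, the rule has a type I error of about 8%

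*Combined protocol and SAP*

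**What the plan says.** Section 3.1 sets the recruitment ceiling: "We will recruit up to 28 participants, including up to 6 pilot participants". Its termination criterion reads: "If results for sound quality ratings are significant after 15 participants completed the rating, we will consider terminating the data collection".

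Section 3.2.1 gives a different range for the analysed number: "Analysis population: 15-25 participants". It describes the unit of evaluation only as "Evaluation group: rating per setting".

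On interim analysis, section 3.2.4 says: "Automatic data analysis is available in the survey tool and will be used throughout the data collection for interim analysis". It adds one adjustment: "Data will be adjusted for repeated measures". The final analysis is in section 3.2.2: "The study manager will analyze the collected data set in R Statistics after the data collection completed".

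The ratings that could trigger the stop are listed in section 2.2.1: "The subjective rating will include rating of reverberation, sound source separation, sound source localization, overall preference ranking and an A/B test for preference".

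**The concern.** A stop on significance at 15, followed by another test if the study continues, gives two chances of a positive result. Without a boundary, the overall error exceeds whatever level is used at each test.

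Three gaps make this more than a missing detail:

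- **Adjustment.** Every participant rates every setting, so an adjustment for repeated measures most naturally means within-person correlation. It names no method for repeated looks.
- **Trigger.** The criterion refers to sound quality ratings in general. The plan does not say which rating, scene or pair of settings must be significant.
- **Final n.** Any boundary needs it, and it could be 22 (28 less 6 pilots), 25 (top of the range in section 3.2.1) or 28 (pilots counted).

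Section 1.1 says the results will inform the compression parameters proposed for new hearing aids. A false or exaggerated preference would therefore shape what the follow-up study tests.

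**Working it through.** **No figure to reproduce.** The plan states no alpha, power, effect size or SD, so there is no calculation of its own to check.

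**Inputs from the plan.** First look at 15 completers (3.1). Final n of 22, 25 or 28 (3.1 and 3.2.1).

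**Assumptions.** One paired comparison, two-sided 5% at each look, no adjustment, and a stop at every significant look.

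**Step 1: normal approximation, two looks.** The test statistics at n = 15 and n = F have correlation √(15/F). The overall error is 1 − P(|Z₁| < 1.96 and |Z₂| < 1.96).

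| Final n (F) | Correlation | Error, normal | Error, paired t-test (simulated) |
|---|---|---|---|
| 22 | √(15/22) = 0.826 | 7.6% | 7.8% |
| 25 | √(15/25) = 0.775 | 8.0% | 8.1% |
| 28 | √(15/28) = 0.732 | 8.2% | 8.3% |

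The simulation used 10,000,000 null trials per cell. A single test in the same simulation gave 5.0%.

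**Step 2: an overall test in place of one pair.** A repeated-measures F test across 4 or 5 conditions, with independent equal-variance errors, gives 7.9% (22), 8.2–8.3% (25) and 8.4–8.5% (28).

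**Step 3: the stop is only considered.** If a significant look leads to a stop with probability q, the error is 5% + q × (two-look error − 5%). For F = 25 and q = 0.5 this is 5% + 0.5 × 3.1% = 6.5%. Simulated across F = 22 to 28, it is 6.4–6.6% for q = 0.5 and 5.7–5.8% for q = 0.25.

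**Step 4: other final numbers and other looks.** If collection ends sooner, the two-look error is 6.2% (n = 16), 7.0% (18) or 7.5% (20). If every participant from 15 on is a look, it is 10.5% (to 22), 11.9% (to 25) or 13.2% (to 28).

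**Step 5: bias.** The plan gives no effect size, so a range is assumed. The average estimate over all trials, with the unadjusted 5% rule at 15 and F = 22 to 28, is:

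| True difference (SD) | Average estimate (SD) |
|---|---|
| 0.2 | 0.21–0.22 |
| 0.4 | 0.43–0.44 |
| 0.6 | 0.63–0.64 |
| 0.8 | 0.82–0.83 |

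**Step 6: candidate boundaries.** Overall error under the null:

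| Boundary (at 15 / at end) | F = 22 | F = 25 | F = 28 |
|---|---|---|---|
| 0.005 / 0.048 | 4.9% | 5.0% | 5.0% |
| 0.030 / 0.030 | 4.8% | 5.0% | 5.1% |
| 0.029 / 0.029 | – | – | 4.9% |

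The 0.005 / 0.048 pair also holds if collection ends at 16 to 20 (4.8–4.9%).

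**The case against.** The strongest objections concern size, and several stand in part.

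- **The plan never states 5%.** True, so 8% is conditional on a conventional level. But two unadjusted looks exceed any level chosen, and the missing alpha is part of the defect.
- **Collection need not reach 22, and 28 exceeds the top of the analysis range.** True. Ending at 16 to 20 lowers the error to 6.2–7.5%, still above 5%.
- **The number of looks is debatable.** One look at 15 is the more natural reading. Interim analysis throughout collection does not exclude more looks, and the error would then be higher.
- **The test is undefined, so exact figures overstate what is known.** Fair. The figures describe one comparison or one overall test. Free choice among several ratings and scenes could add error that is not quantified here.
- **The adjustment for repeated measures might be meant to cover repeated looks.** The wording needs clarifying, but it cannot be credited as alpha control when no sequential method is named.
- **The study is exploratory, stopping is discretionary and a follow-up is planned.** This limits the consequence and keeps the point at a recommendation. It does not remove the inflation: even if a quarter of the stops are taken, the error is 5.7–5.8%.

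**Conclusion.** The concern holds. With two-sided 5% tests, one look at 15, one final analysis at 22 to 28 and every significant look leading to a stop, the type I error is about 8% (7.8–8.3%). Across the other readings it runs from just under 6% (a quarter of stops taken) to about 13% (a look at every participant from 15 to 28). The upward bias is modest: about 0.03–0.04 SD on average at a true difference of 0.40 SD. Confidence is high that the rule lacks error control. The exact size depends on assumptions that the plan leaves open. The change is recommended, not critical.

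**What to change.** Choose one of two changes. Both need SAP wording only and stay within planned recruitment.

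**(a) Remove the significance-based stop.** Suggested text: *The primary analysis is done once, at the end of planned recruitment. Survey-tool output during collection is used for data quality only and not to decide when to stop.* The cost is a forgone saving of up to 7, 10 or 13 participants (22, 25 or 28, less 15).

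**(b) Keep a single look at 15.** Name the rating and comparison, state the planned final n and whether pilots count, rule out further looks, and pre-specify a boundary that holds 5% overall whether or not the stop is taken. The two examples cost the following at a true difference of 0.40 SD:

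| Boundary | Power, F = 22 | F = 25 | F = 28 | Stop early |
|---|---|---|---|---|
| Single analysis at 0.05 | 43.3% | 48.4% | 53.2% | – |
| p<0.005, then p<0.048 | 42.8% | 48.0% | 52.8% | 7% |
| p<0.030 at both looks | 38.4% | 43.3% | 47.8% | 23% |

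If 28 is the final n, the equal boundary should be p<0.029.

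The stricter first look costs at most about 0.5 points of power for true differences of 0.2 to 0.8 SD, but it seldom stops early unless the difference is large: about 2%, 7%, 21% and 44% of trials at 0.2, 0.4, 0.6 and 0.8 SD. The equal boundary stops in about 7%, 23%, 48% and 75%. It costs about 5 points of power at 0.4 SD and 1–2 points at 0.2 and 0.8 SD.

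Under (b), report any estimate after an early stop with a caution about upward bias. A stricter threshold does not remove it: at a true 0.40 SD, the mean estimate among trials that stop is 0.82 with p<0.005 and 0.71 with p<0.030.

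Under either option, say in sections 3.2.1 and 3.2.4 that the repeated-measures adjustment refers to within-person correlation, if that is what is meant.

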3.2 Planned Analyses

3.2.1 Datasets to be analyzed, analysis population

- Analysis population: 15-25 participants
- Evaluation group: rating per setting
- Data sets: subjective ratings
- Additional analyses:
 - individual preferences and their potential dependencies, such as hearing loss, acoustic scenes and previous amplification strategies
 - correction for repeated measures.

3.2.2 Primary Endpoint Analysis

Automatic data analysis is available in the survey tool and will be used throughout the data collection for interim analysis. The study manager will analyze the collected data set in R Statistics after the data collection completed. Microsoft Excel may be used for arranging data and plotting data sets.

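### Nothing ties the test that may close data collection at 15 completers to the R analysis that gives the conclusion

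*Combined protocol and SAP*

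**What the plan says.** The termination paragraph of section 3.1 reads: "If results for sound quality ratings are significant after 15 participants completed the rating, we will consider terminating the data collection". It names no software, test, outcome scale, contrast or significance level.

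Section 3.2.2 describes two analyses. The first runs during collection: "Automatic data analysis is available in the survey tool and will be used throughout the data collection for interim analysis". Section 3.2.4 repeats that sentence and adds "Data will be adjusted for repeated measures". The second comes afterwards: "The study manager will analyze the collected data set in R Statistics after the data collection completed". Section 3.2.3 assigns the secondary analyses to R at the same point.

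Section 3.2.1 gives "Analysis population: 15-25 participants" and lists "correction for repeated measures" among the additional analyses, without a method. On recruitment, section 3.1 says "We will recruit up to 28 participants, including up to 6 pilot participants".

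**The concern.** A stopping rule is useful only if the result that triggers it is the result the trial will report. Here the likely trigger is the output of a survey platform whose method is not described, and the report comes from R with a model that is not described either. The two could differ in outcome, contrast, error term or treatment of the acoustic scenes.

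If the platform's test is the more liberal one, collection may close at 15 on a signal that R then fails to confirm. The plan does not ask for an R check before closing and does not say what happens if the two disagree. Reopening collection at that point would be an unplanned, data-driven step. Under section 1.1 the results are meant to supply compression parameters for an in-person follow-up study, so an ambiguous ending has a practical cost.

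This is a separate matter from how much alpha the look spends. A correct boundary applied to one test does not protect a conclusion drawn from another.

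**Working it through.** **1. The plan's own figure.** The sample size cannot be reproduced. Section 3.1 rests it on precedent ("Previous research with subjective ratings has repeatedly shown that data collected with 15-25 participants can yield significant results") and gives no effect size, SD, alpha or power. If all pilots are excluded, the maximum is 28 − 6 = 22; section 3.2.1 allows up to 25. Both are used as end points in step 4.

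**2. The sections side by side.**
- Section 3.1: significance at 15 completers may end collection. No analysis is named.
- Sections 3.2.2 and 3.2.4: the survey tool is the interim analysis.
- Sections 3.2.2 and 3.2.3: R is run once collection has ended.

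The tool is the only analysis the plan provides at 15 completers, so it is the likely source of the stopping signal. This is an inference, though a strong one. No section equates the two analyses.

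**3. How far apart could they be?** The four scenes match the four stimulus types in section 2.2.1. Every other input is an assumption: n = 15, J = 3 settings, two-sided 0.05, and the model

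y = setting effect + listener + listener-by-setting + residual,

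with residual SD 1, listener SD 1.0, listener-by-setting SD s, and setting effects 0, 0.3 and 0.6.

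- R is taken to test settings against the listener-by-setting mean square: (15 − 1)(3 − 1) = 28 error df, expected value 1 + 4s².
- The tool is taken to fit a participant intercept only, so it pools that term with the within-cell residual. The residual has 15 × 3 × (4 − 1) = 135 df, giving 28 + 135 = 163 error df and an expected value of [28(1 + 4s²) + 135]/163.

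At s = 0.7: R's error term is 1 + 4(0.49) = 2.96. The tool's is (28 × 2.96 + 135)/163 = 217.88/163 = 1.34. The tool's error term is too small by a factor of 2.96/1.34 = 2.21. The last column is simulated.

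| s | R error | Tool error | Ratio | Tool signals R does not confirm |
|---|---|---|---|---|
| 0.7 | 2.96 | 1.34 | 2.21 | about 49% |
| 0.5 | 2.00 | 1.17 | 1.71 | about 35% |
| 0.3 | 1.36 | 1.06 | 1.28 | about 17% |
| 0 | 1.00 | 1.00 | 1.00 | about 7% |

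A repeat run gave 51%, 35%, 16% and 6%. As a cross-check at s = 0.7, the tool is significant in 70-71% of trials and R in 34-35%. Taking R's significant trials as a subset of the tool's, 1 − 34.5/70.5 ≈ 51%. The 7% at s = 0 arises because R has fewer error df (28 against 163). If both analyses use the same error term, the figure is 0% by construction.

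**4. Does alignment settle the matter?** Use the same z-test at 15 and at the final N, each at |z| > 1.96. The two statistics correlate at √(15/N): 0.83 for N = 22 and 0.77 for N = 25. The chance of at least one false rejection is 7.6% and 7.9% respectively. With a look after every participant from 15 onwards it is 10.1% (to 22) and 11.5% (to 25).

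**The case against.** The strongest reply is that the plan shows no conflict. Neither test is specified, section 3.2.4 adjusts the interim data for repeated measures, and section 3.2.1 lists a correction of the same kind. The two may well be handled alike, and using different software for interim and final analyses is not an error. This stands as far as it goes. The repeated-measures wording narrows the gap, but its method is not given and is not linked to the R model. It also concerns correlation within participants and does nothing about repeated looks.

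A reader might infer several stronger things that the documents do not support:
- **That the plan states the stop is taken on the tool's output.** Section 3.1 names no tool.
- **That a significant result at 15 ends the trial irrevocably.** The rule only says termination will be considered. Nothing bars an R check first or a resumption afterwards; neither is planned.
- **That the tool treats every rating as independent.** This would contradict section 3.2.4, so that case is left out of the range.
- **That unconfirmed signals under no true difference are lost answers.** In that case R is correctly rejecting false positives.

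It is also fair to say that the illustration depends on the assumed s, uses three settings where section 2.2.1 also lists a competitor's aid and an unaided recording, and does not cover a tool more conservative than R. Finally, the root cause is that no primary outcome, contrast, model or alpha is defined. Specifying a single test for both purposes would largely remove this point.

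**Conclusion.** The concern holds as a gap in procedure. On the most natural reading, a discretionary stop at 15 completers would rest on the survey tool, while the conclusion rests on R, and the plan neither makes them the same test nor says which governs. A demonstrated difference between the tests is not part of the finding.

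The illustrated size is about 7% to 49% of the tool's stop signals unconfirmed, falling to 0% with a shared error term. This rests on the assumed model and a tool with a participant intercept only. It shows that the risk can be material and does not estimate its rate in this trial. Listener-by-setting variation is plausible, since individual preference is the subject of the secondary objective in section 1.2, but its size is unknown. Because the rule is non-binding and the remedy is cheap, this is a change the plan should make and not a fatal flaw.

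**What to change.** In sections 3.1, 3.2.2 and 3.2.4:

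1. State that any termination decision uses a single data export at 15 completers, run through the same R script, outcome, contrast and model as the final analysis.
2. Lock that script before the export.
3. Limit the tool's automatic output to completeness and data-quality checks, with no part in stopping.
4. State the alpha boundary for the look at 15 and the level left for the final analysis, because items 1 to 3 do not control type I error.

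The cost is that the R script must be written and locked before the 15th completer instead of after the last one, plus one export. Items 1 to 3 need no extra participants. The boundary in item 4 makes an early stop somewhat harder to reach.
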